- HbA1c ≥ 7 and ≤ 11 % (point-of-care machine or local laboratory [i.e. LabCorp]) (*This criteria only applies to the Main Study, it does *not* apply to the Pilot Study*) This can be omitted if it is not possible to go to a laboratory or come to the clinic because of governmental restrictions such as Stay-at-Home orders, in which case there are no entry restrictions based on HbA1c.
- Willingness and ability to comply with scheduled visits and study procedures
- Willingness to comply with all the study devices during the entire trial (i.e. commercially-available CGM, Fitbit, Companion Medical inPen)
- One month stability on insulin parameters prior to enrollment
- MDI users should use Humalog® and Novolog® insulin to use in study insulin pen
- Type 1 diabetes mellitus diagnosed at least one year prior to enrollment in the study as noted by the following:

Criteria for documented hyperglycemia (at least 1 criterion must be met):

- Fasting glucose ≥ 126 mg/dL-confirmed

- Two-hour Oral Glucose Tolerance Test (OGTT) ≥ 200 mg/dL—confirmed hemoglobin A1c (HbA1c) $\geq 6.5\%$ and documented by history – confirmed Random glucose ≥ 200 mg/dL with symptoms
- No data at diagnosis is available but the participant has a convincing history of hyperglycemia consistent with diabetes

Criteria for requiring insulin at diagnosis (at least 1 criterion must be met):

- Participant required insulin at diagnosis and continually thereafter
- Participant did not start insulin at diagnosis but upon investigator review likely needed insulin (significant hyperglycemia that did not respond to oral agents) and did require insulin eventually and used continually
- The diagnosis of type 1 diabetes mellitus does not require documentation of C-peptide level or islet cell antibody positivity.
- Commitment to maintaining uninterrupted availability via cell phone at all times
- No diabetes complications
- Participants must demonstrate English proficiency and proper mental status and cognition for completion of the study.

- Not currently known to be pregnant, breast feeding, or intending to become pregnant (females). A negative urine pregnancy test will be required for adolescent girls who are able to become pregnant. Participants who become pregnant will be discontinued from the study.
- Ability to access the Internet to provide data to the clinical team or to travel to the research center so that the study equipment can be downloaded.

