Study Objectives & Endpoint Definitions:

As mentioned previously, this project seeks to assess how CloudConnect affects participant engagement, dyad engagement, and clinical outcomes in adolescent T1D.

We will assess how adolescents and their parent(s)/guardian(s) respond to this new approach using the Family Communication Inventory (FCI). This diabetes-specific approach was designed by the investigators to assess parent-child communication regarding tasks (discussion of insulin dosing for a given meal, BG trends, need for dose changes). As an outcome measure, scores for parents and adolescents are summed, with higher scores representing higher degree of engagement and T1D-specific communication.

Power/Precision of the study to address major study endpoints:

In using the FCI, we determined based on preliminary data from 220 adolescent/parent participants eligible for the study, with mean (90.3) and standard deviation (12.5) that we are powered to detect a difference of 8.5% in this outcome in the treatment group with 80% power and an alpha of 0.05. This study will require 40 adolescent participants with 40 parent(s)/guardian(s) to complete per arm. Assuming a non-adherence/drop-out rate of 20-30% for Intention-to-Treat (ITT) analysis, 55 participants is yielded per arm.

3. Provide a justification for the sample size used in this protocol.

The study team will attempt to enroll an equal number subjects based on gender, CSII, and MDI use. The study is powered to detect a difference of 8.5% in this outcome in the treatment group with 80% power and an alpha of 0.05. This study will require 40 adolescent participants with 40 parent(s)/guardian(s) to complete per arm. Assuming a non-adherence/drop-out rate of 20-30% for Intention-to-Treat (ITT) analysis, 55 participants is yielded per arm.

4. What is your plan for primary variable analysis?

Because this is a randomized study, our primary outcome (score on the Family Communication Inventory) will be by t-test comparing those randomized to CloudConnect to usual care+CGM. Comparison of secondary outcomes between treatment groups will also be t-tests. Secondary analyses of both the primary and secondary outcomes will utilize multivariable ANOVA, particularly in the event that key variables differ between groups. For example, if average steps per day [as a measure of exercise] is higher in one group vs.

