another, this will be used as a variable in the comparison of mean glucose by CGM to evaluate whether there remained a difference in mean glucose once total daily steps was taken into account. Similarly, if there is an imbalance of key participant characteristics among participants who complete the study in one treatment group (such as higher proportion of multiple-daily-injection participants in the CloudConnect group), this will be considered as a variable in the multivariable ANOVA comparing mean glucose by CGM, as a secondary analysis.

5. What is your plan for secondary variable analysis?

- HbA1c
- Mean glucose by CGM
- Percent time in range 70-180 mg/dL
- Percent time in range 70-150 mg/dL
- Percent time <70 mg/dL
- Percent time >180 mg/dL
- Number of low BG
- Average daily insulin dose
- Average grams of carbohydrate entered
- Steps/day by Fitbit
- Questionnaires: Family Conflict Scale, Division of Diabetes Responsibilities, Child Self Management and My-Q scores.
- Response to weekly standardized questions:
 - i. *During the past week, did you talk with your parents about your diabetes management?*
(Yes=1, No=2)
 - ii. If you answered “yes,” how good or bad was the tone of that conversation?
(Likert scale: Very good = 1; good =2; Neutral = 3 bad =4; Very bad =5)
 - iii. During the past week, did you change your insulin parameters?
(Yes=1, No=2)

6. Have you been working with a statistician in designing this protocol?

No

7. Will data from multiple sites be combined during analysis?

No

Study Procedures-Biomedical Research

1. What will be done in this protocol?

PILOT STUDY:

Up to six adolescent subjects and six parent(s)/guardian(s) will be enrolled in a Pilot Study to assess the components used by the Experimental Group of the Main Study. This trial will evaluate if: (i) subjects can be trained to use study CGM + study Fitbit + personal pump (if pump user) or study insulin pen for mealtime

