 - On a scale of 1-7, with 1 being not at all useful and 7 being very useful, how useful were the weekly reports in helping you communicate with your parents/child about managing your/your child's diabetes? Can you tell me why you gave the score you did? What could have made the weekly reports more useful to you?
 - Is there anything else you would like to tell us about your experience with the weekly reports?

The weekly contact by phone, email or text for both the Control and Experimental Groups will be to:

- Check for AE or SAE
- Remind to download all the data (i.e. CGM, insulin pump/insulin pen, Fitbit data)
- Ask standardized questions, which will include the following:
 - For the child participant:
 - During the past week, did you talk with your parents about your diabetes management?
Yes or No
 - If you answered "yes," how good or bad was the tone of that conversation?
(Likert scale: Very good good Neutral bad Very bad)
 - During the past week, did you change your insulin parameters?
(Yes=1, No=2)
 - For the adult participant:
 - During the past week, did you talk with your child about his/her diabetes management?
Yes or No
 - If you answered "yes," how good or bad was the tone of that conversation?
(Likert scale: Very good good Neutral bad Very bad)
 - During the past week, did your child change his/her insulin parameters?
(Yes=1, No=2)

(Yes=1, No=2)

Visit 1: Adolescent subjects will be screened as indicated in the inclusion/exclusion criteria, and the consent form will be signed electronically after all the question related to the study are answered. The consenting process may occur over the phone/video or in-person. Demographic information and medical history information will then be obtained. A physical exam can either be performed at Visit 1 or documentation of a physical exam at a physician/provider visit within one year will suffice. Hemoglobin A1c will be collected with point-of-care equipment or at a local laboratory. This can be omitted if it is not possible to go to a laboratory or come to the clinic because of governmental restrictions such as Stay-at-Home orders. A urine pregnancy test will be required for adolescent girls who are able to become pregnant. Test must be negative to participate in the study.

If the adolescent subject meets eligibility, visit 1 and 2 may be combined. A repeat Hemoglobin A1c will be collected if visit 1 and 2 are greater than 28 days.

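### The main comparison of four CGM glucose outcomes is an unadjusted t-test, which gives up precision that pre-specified adjustment for entry HbA1c could recover

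*Combined protocol and SAP*

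**What the plan says.** Statistical Considerations, item 4, sets the main test for everything other than the primary questionnaire score: "Comparison of secondary outcomes between treatment groups will also be t-tests". Item 5 lists the CGM outcomes among the secondary variables, including mean glucose, "Percent time in range 70-180 mg/dL", percent time 70-150 and percent time >180 mg/dL.

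Item 4 then adds an adjusted analysis: "Secondary analyses of both the primary and secondary outcomes will utilize multivariable ANOVA, particularly in the event that key variables differ between groups". Two examples follow, both for mean CGM glucose. The first is average steps per day: if it differs between arms, "this will be used as a variable in the comparison of mean glucose by CGM". The second is insulin delivery method, to be added "if there is an imbalance of key participant characteristics among participants who complete the study in one treatment group". HbA1c is not named as a covariate in either example or elsewhere.

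Entry HbA1c is nevertheless part of the plan. Eligibility for the Main Study requires "HbA1c ≥ 7 and ≤ 11" percent, and under Visit 1 "Hemoglobin A1c will be collected with point-of-care equipment or at a local laboratory". It is repeated if Visits 1 and 2 are more than 28 days apart. Both places let it be omitted when governmental restrictions prevent a clinic or laboratory visit, and in that case no HbA1c entry limits apply. Randomisation is stratified by age group and insulin therapy, not by HbA1c.

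**The concern.** Participants may enter anywhere between 7 and 11% HbA1c, so their average glucose before the trial differs widely. They keep their own insulin and insulin parameters during the trial, and the experimental element is a weekly report. Part of the between-person spread in on-study glucose is therefore likely to reflect where each person started. An unadjusted t-test leaves that part in the error term.

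No CGM baseline is available to take its place. The one-week run-in is described under Visit 2 for CGM-naïve participants, may be skipped by those with CGM experience, and is kept out of the 12-week data.

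At stake is the ability to see a glucose effect. Clinical outcomes are part of the second specific aim, but the sample was sized only for the Family Communication Inventory, and no power is stated for any CGM outcome. An adjusted model chosen after the results are known would carry less weight than one fixed beforehand.

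**Working it through.** **Inputs from the documents.** Item 2 of Statistical Considerations gives 40 completers per arm, alpha 0.05, 80% power, and an inventory mean of 90.3 with SD 12.5. Two-sided testing is assumed, because sidedness is not stated.

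**The plan's own figure.** Reading 8.5% as relative to the mean, 0.085 × 90.3 = 7.68 points, and 7.68 / 12.5 = 0.614 SD. The normal formula n = 2(1.960 + 0.842)² / 0.614² gives 42 per arm, and 40 per arm gives 78.4% power. The stated 40 is reproduced closely enough to use as the base.

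**Unadjusted comparison of a CGM outcome.** The documents give no SD for these outcomes, so results are in SD units. The detectable difference is (1.960 + 0.842) × √(2/40) = 0.626 SD by the normal formula, and 0.634 SD with the exact t distribution.

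**Adjusted comparison.** If entry HbA1c has within-arm correlation r with the outcome, the residual variance is multiplied by 1 − r² and the standard error by √(1 − r²). The documents give no value for r, so the range is an assumption. Results use the exact t distribution with one degree of freedom lost:

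| r (assumed) | Residual variance | Detectable difference, 80% power | Power at 0.634 SD | Equivalent n per arm for a t-test, 40/(1 − r²) |
|---|---|---|---|---|
| 0 (t-test) | 1.00 | 0.634 SD | 80% | 40 |
| 0.3 | 0.91 | 0.605 SD | 83.6% | 44 |
| 0.4 | 0.84 | 0.581 SD | 86.4% | 48 |
| 0.5 | 0.75 | 0.549 SD | 89.9% | 53 |
| 0.6 | 0.64 | 0.508 SD | 93.8% | 62.5 |
| 0.7 | 0.51 | 0.453 SD | 97.5% | 78 |

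By the normal formula the detectable difference is 0.598 SD at r = 0.3 and 0.447 SD at r = 0.7. A 4,000-run simulation agreed on power: 83%, 90% and 97% at r = 0.3, 0.5 and 0.7.

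**Missing entry values.** Suppose a fraction m lacks entry HbA1c and is kept by mean imputation plus an indicator. The residual variance is then about 1 − (1 − m)r², assuming the same outcome variance in those with and without the value. Taking m = 20% (assumed):

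- r = 0.3: 1 − 0.8 × 0.09 = 0.928, power about 83%
- r = 0.5: 1 − 0.8 × 0.25 = 0.80, power about 88%
- r = 0.7: 1 − 0.8 × 0.49 = 0.608, power about 95%

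With m = 40% and r = 0.3, the variance is 1 − 0.6 × 0.09 = 0.946 and power is about 82%, close to no gain.

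**Cost if HbA1c predicts nothing.** At r = 0 with 20% missing, simulated power was 77% against 79% for the t-test.

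**The case against.** The strongest reply is that nothing here is an error. Randomisation makes the unadjusted t-test valid, these are secondary outcomes, and the sample size for the primary outcome is untouched. That stands. A reader might infer that the glucose comparisons are biased or have an inflated false-positive rate. The documents do not support that.

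A reader might also infer that a chance difference in starting control would go uncorrected. That is too strong. Item 4 says the ANOVA is used particularly, not only, when arms differ, and its named characteristics are examples, so starting control could be adjusted for. What remains is narrower: that analysis is secondary, depends largely on imbalance seen among completers, and leaves the covariate to be chosen later. One of its examples, steps per day, is measured after randomisation and is itself a listed outcome.

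The Objectives/Hypothesis section also says both approaches will be compared with the diabetes control experienced before the intervention. This shows that prior control was thought relevant, but it is not a covariate-adjusted comparison between arms.

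The size can be challenged too. The documents give several reasons why r could be low: the 7-11% entry range, the improvement expected from new access to CGM, the requirement that closed-loop users switch that function off, and HbA1c measured either at the point of care or in a laboratory. These justify starting the range at 0.3, where the gain is modest. They also mean that HbA1c cannot be called the strongest available predictor on the documents' evidence.

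Finally, nothing in the documents shows that missing entry values will be few. Participants admitted under the waiver face no HbA1c limits and may vary more than the others, so the missing-data figures may be optimistic.

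**Conclusion.** The point holds as a loss of precision in the main comparison of four secondary outcomes: mean CGM glucose and percent time 70-180, 70-150 and >180 mg/dL. With 40 completers per arm and an assumed r of 0.3 to 0.7, adjustment for entry HbA1c would lower the detectable difference from 0.63 SD to about 0.60-0.45 SD and raise power at 0.63 SD from 80% to about 84-97%. The low end is a small improvement and the high end a substantial one; the documents cannot say which applies. The gain shrinks as more entry values are missing.

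It would be wrong to extend this to every CGM outcome. Percent time <70 mg/dL and the number of low glucose values may be only weakly related to entry HbA1c, and no gain is claimed for them. The change is worth making because the covariate is already collected and the possible loss is at most about two percentage points of power in the case simulated.

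**What to change.** In items 4 and 5 of Statistical Considerations, make the main between-arm comparison of these four outcomes a linear model with arm and Visit 1 HbA1c, using the repeat value if it was redrawn. State that the model applies whether or not the arms look imbalanced. Keep dyads with no entry HbA1c by imputing the overall mean, ignoring arm, and adding a missing-value indicator. Report the unadjusted t-test as a sensitivity analysis, and fix this wording before any outcome data are compared by arm.

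The change needs analysis wording only, with no new data or visits. Its costs are a linear-model assumption, a missing-value rule whose reach is unknown because the number of waived tests is unknown, and a negligible loss of power if r is near zero.

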The first of two studies associated with this proposal was a needs assessment study that reveals patients' and primary informal caregivers' needs/preferences for the technology core of Cloud Connect (UVA IRB-SBS #2016-0273). This second study will implement, a system that aggregates blood glucose values, exercise, insulin, and meal information collected from individuals with T1D. This information is then analyzed to determine if there are areas of hypo and hyperglycemic risk and how those risk zones may relate to physical activity and insulin dosing behavior. From that analysis, a report is generated and sent to the adolescents and their parents/guardians on a weekly basis giving them insight into how they can increase their ability to control their blood glucose values.

The results of this project will inform the design information technology that improves engagement and clinical outcomes for patients who require continuous monitoring and who engage an informal primary caregiver in self-management outside clinical settings.

Objectives/Hypothesis

The research project proposed here seeks to assess an approach to self-management called CloudConnect, evaluating the impact of CloudConnect on patient engagement, dyad engagement, and clinical outcomes in adolescent T1D.

This assessment will address the essential question of how adolescents and their parent/guardian respond to this new approach to self-management. This study is designed to assess the impact of a T1D-specific CloudConnect implementation on patient engagement, dyad engagement, and clinical outcomes as well as the relationships among these outcome measures for adolescents with diabetes. Throughout this protocol, 'the subject' will refer to the dyad of an adolescent and one parent/guardian.

The randomized controlled trial of CloudConnect is intended to compare the impact of this new model of self-management with use of their personal insulin parameters with the addition of continuous glucose monitoring (CGM) and Fitbit, if not already in use by subject. Assessment between the study subject/parent using validated surveys and assess clinical outcomes including HbA1c, number of hypoglycemic events, etc. over the 3-month period.

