Both groups will participate in the same number of visits (completed either in clinic or via phone or video conferencing) and follow up communication contacts done by phone calls, text messages and/or emails during the entire length of the trial. The production of the CloudConnect Report, in combination with the available Dexcom alarms and apps, is the study differential between groups.

*Secondary health outcomes: Average Blood Glucose values by Continuous Glucose Monitor; average total daily insulin; average carbohydrate of grams entered; number of insulin boluses; average number of steps by day

Figure 1: Study Design

There are four visits in the Main Study. Visit 1 and 2 may be combined and may be in person or via phone or video conference. A repeat Hemoglobin A1c will be collected if visit 1 and 2 are greater than 28 days. Visit 3 may be completed by phone. In addition, there will be weekly communication done by phone call, text message and/or email throughout the entire 12 weeks (3 months) of the data collection portion of the study. Method of weekly communications with the adolescent and parent will be based on participant/parent preference. The study team will communicate separately with the child and the parent in order to obtain their feedback independent of the other.

Subjects will be asked to electronically complete the following questionnaires at the completion of Visit 1 and repeated again at the conclusion of their study participation. Questionnaires may be answered remotely (i.e. at home) within a week of the visit or during a CRU visit.

- Blood Glucose Monitoring Communication questionnaire (Hood et al Diab Care 2004)
- Child and Parental Responsibility Questionnaire (adapted from Anderson et al J. Ped Psychol 1990)
- Child Self-Management
- Diabetes Care and Communication
- Diabetes Family Conflict Scale-Revised (Hood et al Diab Care 2007)
- Family Communication Inventory

- MY-Q (deWit et al Ped Diab 2012)
- Questions about CloudConnect use (CloudConnect group only, asked only at study end):
 - On a scale of 1-7, with 1 being very difficult and 7 being very easy, how easy was it to understand the information provided in the weekly reports? Can you tell me why you gave the score you did? What could have made the weekly reports easier to understand?

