Visit 2 (may be combined with Visit 1, may be done via phone or video): Adolescent subjects will be randomized and trained on the use of the study CGM and Fitbit. The CGM will be inserted into their abdomen per manufacturer instructions. Both Control and Experimental Group subjects will use their own personal pump. If the subject uses multiple daily injections (MDI), a commercially available Bluetooth connected insulin pen (inPen) will be given to both the Control and Experimental subjects in order to be able to collect the data accurately about meal time bolus treatments. Both pump users and MDI subjects will use their personal insulin. Each group will provide the study team weekly downloads from the study equipment and the personal insulin pump. Weekly CloudConnect reports will be provided to the Experimental Group participants *only*.

Depending on the subjects/family preference, the study team contact subjects via phone calls, text messages and/or emails at least once a week during the trial to:

- a) Remind them to download and transmit the data
- b) Check for AEs or SAEs
- c) Ask weekly standardized questions

All subjects will be reminded on how to download study data, if necessary. Both groups may complete a 1-week run-in period if they are CGM-naïve to ensure they are comfortable with the use of the study equipment, that all the study devices work properly, and to address issues related to transmission of the data to the study team. This run-in period may be repeated as necessary up to 3 times at the request of the study subject or study team. This data will not be included as part of the 12 week data collection. For subjects who have CGM experience, the investigator will determine if it is appropriate for he or she to skip the run-in period.

Visit 3 Check-in (Week 8 / on-site, email, or phone):

Subjects will download diabetes equipment weekly and submit the data to the study team for 12 weeks. Subjects may be asked to repeat a week of data collection if the quality of the data is insufficient for analysis.

A Check-In with the adolescent and parent/guardian will be completed to evaluate compliance and to answer any questions that the adolescent or parent may have about the study.

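### The secondary mean-glucose model may adjust for steps per day, a post-randomisation outcome; if CloudConnect changes activity, the adjusted difference is not its total effect

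*Combined protocol and SAP*

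**What the plan says.** Statistical Considerations, item 4, sets the FCI score as primary outcome, tested by t-test, and adds: "Comparison of secondary outcomes between treatment groups will also be t-tests". Multivariable ANOVA is reserved for secondary analyses, chiefly when key variables differ between the arms.

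Two illustrations follow. In the first, "if average steps per day [as a measure of exercise] is higher in one group vs" the other, then "this will be used as a variable in the comparison of mean glucose by CGM", to see whether a glucose difference survives once steps are accounted for. The second is introduced as similar: "if there is an imbalance of key participant characteristics among participants who complete the study in one treatment group", that characteristic will be considered for the model. Its example is insulin therapy.

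Steps appear elsewhere as an outcome: "Steps/day by Fitbit" in item 5, and "average number of steps by day" among the secondary health outcomes listed with Figure 1. At Main Study Visit 2, "Adolescent subjects will be randomized and trained on the use of the study CGM and Fitbit".

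**The concern.** Adjusting a randomised comparison for a baseline variable leaves its target unchanged and usually improves precision. Adjusting for something the intervention may have altered changes the target. The plan puts a post-randomisation outcome beside a baseline characteristic and treats an arm difference in either as an imbalance to be allowed for.

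The condition for adjusting adds to the problem. Steps enter when the arms differ on them, and that is more likely when CloudConnect has changed activity. What counts as higher is not defined.

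The t-test and the ANOVA could then disagree, and the plan does not say that they answer different questions. A reader could take a null adjusted result as evidence that CloudConnect does not affect glucose. Clinical outcomes are a stated objective of the trial, so this reading matters.

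**Working it through.** **Is the step count a baseline variable?** Nothing in the text makes it one. The Fitbit is introduced at the visit where participants are randomised. The run-in is described under that same visit, and its data are kept out of the 12-week collection. The Objectives allow that some participants already use a Fitbit, but no pre-randomisation step count is described.

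**Could CloudConnect change steps?** Plausibly. The Background section says the system analyses areas of glucose risk and "how those risk zones may relate to physical activity and insulin dosing behavior", and the weekly report built on this goes to the Experimental Group only. The protocol does not predict a change in steps.

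**Algebra.** The plan gives no figure to reproduce here. Let U be an unmeasured factor such as motivation, with steps scaled to a within-arm SD of 1:

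- steps = d × arm + l × U + noise
- glucose = c × arm + b × steps + g × U + noise

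The total effect, which the t-test estimates, is c + b×d. The within-arm slope of glucose on steps is b + l×g. The adjusted difference is therefore (c + b×d) − (b + l×g)×d = c − d×l×g. It equals the total effect when d = 0. When d is not 0, it loses b×d and gains −d×l×g.

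**Inputs.** The 40 completers per arm come from the sample-size section. The glucose SD of 35 mg/dL and all of d, b, c, l and g are assumptions, because the documents give none. Rejection rates are at two-sided 0.05, from at least 4,000 simulated trials per scenario.

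| Scenario (mg/dL) | Total effect | Adjusted difference | Rejection, unadjusted → adjusted |
|---|---|---|---|
| 1. d=0, b=−20, c=−10 | −10 | −10 | 24% → 32% |
| 2. d=0.5, c=0, b=−5 / −10 / −20 | −2.5 / −5 / −10 | 0 / 0 / 0 | not shown |
| 2a. d=0.25, c=0, b=−20 | −5 | 0 | not shown |
| 3. d=0.5, c=−10, b=−20 | −20 | −10 | 72% → 33% |
| 3a. d=0.5, c=−10, b=−10 | −15 | −10 | 48% → 24% |
| 3b. d=0.5, c=−10, b=−5 | −12.5 | −10 | 35% → 23% |
| 4. d=0.5, b=c=0, l=0.5, g=−5 / −10 / −20 | 0 | +1.25 / +2.5 / +5 | adjusted: about 5% / 6% / 10% (nominal 5%) |

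Simulated means agree with the formulas. For scenario 1 they were −9.9 both ways. For scenario 2 with b=−20 they were −10.1 unadjusted and −0.1 adjusted.

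**Hand check of scenario 3.** The unadjusted standard error is 35 × √(2/40) = 7.83, and 20/7.83 = 2.56, which gives about 72% power. The adjusted residual SD is √(35² − 20²) = 28.7. Its standard error is 28.7 × √(2/40) × √(1 + 0.5²/4) = 6.62, and 10/6.62 = 1.51, which gives about 33%.

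**How often steps would enter.** If higher means p<0.05 on steps, the expected z is d/√(2/40). That is 0.5/0.224 = 2.24 (about 60% of trials), 0.25/0.224 = 1.12 (about 19–20%), or 0 (5%). If any numerical difference counts, steps enter almost always.

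**The case against.** The strongest reply is that the plan already poses a conditional question: does a glucose difference survive once steps are taken into account? It nowhere calls the result CloudConnect's total effect, which the t-test still estimates. The objectives also cover relationships among outcomes. This is fair, and it makes the defect one of interpretation. But the plan neither calls the model a mediation analysis nor states the assumption such an analysis needs, and it pairs steps with a baseline characteristic as though both were imbalances to be allowed for.

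The steps sentence is an example, in a secondary analysis, of one secondary outcome, and no passage predicts a change in steps. All of that stands and limits the weight of the point. The example is nevertheless the only worked instruction for a post-randomisation variable, and an analyst would follow it.

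The largest power loss rests on a strong slope: −20 mg/dL per SD means steps explain (20/35)² = 33% of within-arm glucose variance. The losses at −10 and −5 are smaller, as shown. Adjustment can also help. With no shift and that slope, power rises from 24% to 32%, and among trials where p<0.05 brings steps in, the root mean squared error for the total effect falls from about 12–13 to 6–7 mg/dL. With a 0.25 SD shift the gain is small (9.2 to 8.4). At 0.5 SD adjustment is worse. The benefit therefore depends on the shift being absent or small, which cannot be known in advance.

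The order of run-in and randomisation is not fully explicit. Even if run-in came first, it is needed only for CGM-naïve participants, and the plan does not use its data as a baseline.

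Finally, part of the remedy concerns baseline questionnaires and HbA1c rather than steps. That is true. It is included because a rule that removes one set of covariates should name their replacement.

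**Conclusion.** The concern holds, with high confidence in the reading of the text and the algebra. It is a should-fix point: the primary FCI comparison and all the main t-tests are untouched, and only the secondary adjusted glucose result is affected.

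The bias depends on CloudConnect changing steps, and its size in this trial cannot be computed. Under the assumed inputs with a step shift of 0.25 or 0.5 SD, adjustment removes 2.5 to 10 mg/dL of true effect, or creates a spurious difference of 1.25 to 5 mg/dL where there is none. False rejection stays near nominal except at the strongest assumed confounding, where it is about 10%.

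A lesser point is that the second illustration also chooses covariates by observed imbalance, and among completers. Its example, insulin therapy, is a legitimate covariate because it is fixed before randomisation.

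**What to change.** In item 4, restrict the adjusted between-arm models to covariates fixed before randomisation, included whatever imbalance is seen:

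- **All models:** age group and insulin therapy (the stratification factors) and prior CGM use.
- **FCI and other questionnaires:** the Visit 1 score, completed before randomisation. The protocol allows completion up to a week after the visit, which can fall after randomisation when Visits 1 and 2 are combined, so add an instruction on timing.
- **HbA1c and CGM glucose outcomes:** the last HbA1c before randomisation, since no pre-randomisation CGM period is planned. Where HbA1c was omitted under the stay-at-home provision, use mean imputation with a missing-value indicator.

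Delete the steps example and the completer-imbalance condition as ways of choosing covariates. If a steps-adjusted glucose model is still wanted, report it as exploratory mediation, state its no-unmeasured-confounding assumption, and say that it does not estimate the total effect.

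The cost is analysis wording, one rule for missing HbA1c and one instruction on questionnaire timing, with no new visit or measurement. The downsides are that HbA1c is only a proxy for baseline CGM glucose, some values will be missing, and a combined Visit 1/2 may run slightly longer.
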